5 RISK ASSESSMENT

The Restora Nasal Spacer has the primary mode of action of being a mechanical support to physically separate opposing mucosal surfaces and thereby reduce the potential for synechiae formation. The addition of Mometasone Furoate, a well-known and well characterized anti-inflammatory with a long history of use in the nasal cavity, is intended to reduce post-surgical inflammation during the natural healing process.

There are two potential sources of risks that can be derived from the use of the Restora spacer: 1) due to the spacer material and shape and 2) due to the drug loaded onto the spacer.

The risks associated with the spacer material itself is considered minimal as the material is biocompatible for its intended use and the material shape (thickness, and area) is similar to that of the standard Silastic Silicone sheet that is used surgically.

The risk associated with the drug is comparable to that with the use of the commercially available Intersect Propel Stent as the amount of drug that is expected to be released from Restora™ is similar to that released from Propel, 370µg. In addition, the anti-inflammatory steroid, Mometasone Furoate (active ingredient in Nasonex) has been approved for intra-nasal delivery since 1997. The recommended daily dose delivered for treatment of nasal allergies is 2 sprays per nostril per day and for polyposis is 2 sprays per nostril twice a day. Each spray dose is 50 µg. Therefore, the total maximum recommended dose for the patient is 400 µg per day, and total of 2,800 µg over a 7 day period. Topical Mometasone Furoate spray has also been administered post ESS to help reduce post surgical inflammation at the same dose prescribed for allergies, namely 400 µg/day (14). Compared with this spray dose, the dose of Mometasone Furoate delivered by Restora is at least 7 fold less than that for the Nasonex.

The Restora Nasal Spacer is considered a non-significant risk device because it does not meet the criteria specified by FDA for a significant risk device. Reference FDA Guidance "Information Sheet Guidance for IRBs, Clinical Investigators, and Sponsors – Significant Risk and Non-Significant Risk Medical Device Studies" dated January 2006:

- Restora is not intended as a permanent implant and does not present a potential for serious risk to the health, safety, or welfare of a subject;
- Restora is not purported or represented to be for use supporting or sustaining human life and does not present a potential for serious risk to the health, safety, or welfare of a subject;
- Restora is not for a use of substantial importance in diagnosing, curing, mitigating, or treating disease, or otherwise preventing impairment of human health and does not present a potential for serious risk to the health, safety, or welfare of a subject; and
- Does not otherwise present a potential for serious risk to the health, safety, or welfare of a subject

This study will be conducted in accordance with requirements specified in 21 CFR 812.2(b).

Risks associated with the use of the SinuSys Restora Spacer are anticipated to be similar to those experienced by patients undergoing placement of other non-resorbable spacers and less than that of Propel due to its non-resorbable nature. The potential clinical benefits of the Restora Spacer are believed to exceed any residual risks associated with the use of the Restora Spacer.

6 STUDY OBJECTIVE

The main objective of the trial is to evaluate basic device usability and confirm safety and effectiveness of Restora™ Mometasone Furoate eluting spacer as compared to a Silastic spacer.

7 RESTORA AND SILASTIC SPACERS DESCRIPTION

Silastic spacer is an inert plastic that can be shaped to fit the operative field. A soft, pliable, 0.04 -inch-thick polymeric Silastic sheet, shaped into an inverted U by suturing the middle of the spacer to keep the shape, will be placed between the middle turbinate and lateral nasal wall. Image of Silastic spacer placed in the Middle Meatus is shown in figure 1.

Figure 1: Silastic Nasal Spacer placed in the Middle Meatus of the nose.

Restora spacer is composed of Tecophilic HP-93A-100 resin (Lubrizol Inc) that has been extruded, cut to the desired shape, shaped, packaged, and finally exposed to a terminal gamma irradiation (25-40 kGy) sterilization process to reduce bioburden. The material is provided in a boot shape geometry and has

thickness of approximately 0.84mm (Figure 1). The Restora spacer is pre-shaped into an inverted U to keep the shape before placement between middle turbinate and lateral nasal wall.

Figure 2: Restora Nasal Spacer placed in the Middle Meatus of the nose.

Mometasone Furoate will be loaded into the spacer using proprietary SinuSys protocol to target up to 370 μgm delivery in-vivo. Once loaded, the spacer is capable of eluting drug over its residency time in the middle meatus.

7.1 Preclinical data

The Restora spacer has been tested in the USP dissolution apparatus in comparison to Intersect Propel stent. In order to do the side by side comparison, Restora spacer was loaded with the same amount of MF as Propel, 370 μgm . Figure 3 below demonstrates controlled sustained release of Mometasone Furoate as % of total drug loading.

[figure not shown]

Figure 3: Cumulative Mometasone Furoate Release from Propel Mini compared to Restora Nasal spacer

This graph demonstrates that Restora platform has capacity to provide longer sustained release than the Propel product under same test conditions.

7.2 Clinical data

Initial experience with Restora Spacer has been completed on 23 patients, as part of on-going study by [name] at University of British Columbia ([name] MD, Principal Investigator), under similar protocol. In this study, patients undergoing ESS procedure received one Restora Spacer and one Silastic spacer, placed bi-laterally, post ESS. The spacers were removed at day 6 post surgery. There were no adverse events reported.

Spacers were sent to SinuSys for MF content analysis. The average amount of MF loaded on the spacers was 483.64 ± 25.62 μgm . Average amount of drug remaining on the spacers was 418.83 ± 25.65 μgm . Total amount of drug released was 64.81 μgm , 13% of the dose loaded.

Based on this information, loading protocol used in this study is adjusted to provide target dose of up to 370 μgm in vivo.

8 STUDY DESIGN AND ENDPOINTS

Approximately 50 patients will receive spacers during their ESS procedures and be followed for 90 days. This will require enrolling approximately 60 patients between all of the participating centers to account for possible loss-to-follow-up (LTf).

- **Primary Endpoint**
 - 35-day sinonasal mucosal inflammation assessed by rigid endoscopy and graded on Lund-Kennedy sinus mucosal endoscopic staging system
- **Secondary Endpoints**
 - 90-day post ESS incidence of middle meatal synechiae
 - 35 and 90-day sinonasal mucosal inflammation assessed by rigid endoscopy and graded on Lund-Kennedy sinus mucosal endoscopic staging system
 - 35 and 90-day intraocular pressure (IOP) assessed using applanation tonometry and compared to baseline IOP obtained preoperatively
 - 35 and 90-day post-ESS incidence of middle meatal synechiae
 - 90-day validated Sinonasal Outcomes Test-22 (SNOT- 22) scores
 - 35-day frequency of postoperative interventions, including lyses of adhesions and debridement.
 - 35-day frequency of oral steroid rescue
 - 35 days middle turbinate position

8.1 Inclusion Criteria

- 1) Age between 18 and 75 years

- 2) Diagnosis of chronic rhinosinusitis (CRS), per current guidelines
- 3) Patients who need to undergo primary bilateral complete endoscopic sinus surgery
- 4) Subject has the ability to follow the study instructions, is willing to be available on the specific required study visit days, and is willing to complete all study visit procedures and assessments
- 5) Subject must understand the research nature of this study and sign an informed consent prior to the performance of any study-specific procedure or assessment

8.2 **Exclusion Criteria**

- 1) Subject is pregnant or breast feeding
- 2) Patients with sino-nasal tumors
- 3) Patients solely undergoing nasal septal reconstruction
- 4) Patients with previous history of endoscopic sinus surgery
- 5) Cystic fibrosis or syndromic patients
- 6) Patients with autoimmune diseases
- 7) Patients who have taken oral steroids less than 30 days prior to surgery
- 8) Patients with a history or diagnosis of glaucoma or ocular hypertension
- 9) Any other circumstance or condition that in the Investigator's opinion causes the subject to be an inappropriate candidate for participating in this study

8.3 **Blinding**

The study is double-blinded. Each patient is his or her own control. Neither the patient nor the assessor will know on which side the respective spacer is placed. The Principal Investigator will be the blinded assessor. The choice of spacer for each side will be randomized using the sealed envelope system.

8.4 **Study Procedures**

A table of study assessments is presented in Appendix A.

8.5 **Screening/Enrollment Visit**

All consented subjects will be assigned a unique subject number. Screening procedures can occur only after consent is signed. Screening and device placement may occur on the same day. If the placement procedure occurs on a different day than the screening/enrollment visit the inclusion/exclusion criteria have to be reevaluated. The device placement attempt must occur within 30 days of initiating screening procedures.

As a standard of care, all patients will fill out the SNOT-22 quality of life questionnaire at this visit.

8.6 **Screening Procedures**

The following screening procedures will be performed before the device placement attempt is initiated:

1. Written informed consent prior to conducting any study-specific procedures
2. Demographic information
3. Targeted medical history
4. Medication history including medications for 7 days prior to enrollment
5. Pregnancy test
6. Nasal Endoscopy
7. Any other screening procedures for dilation of intended treatment spaces that are standard of care to the investigation site
8. Review of eligibility criteria (subject failing to meet all inclusion/exclusion criteria are to be recorded as Screen Failures)

8.7 Treatment visit

Patients will undergo bilateral ESS procedure. Each patient will receive one Silastic and one Restora spacer, placed bilaterally.

As a standard of care all patients are treated with oral antibiotics (clavulin or clindamycin if allergic to penicillin) while they have spacers inserted into their nose.

The device(s) can be removed anytime upon the subjects' request or if the Investigator deems it necessary.

8.8 Follow-up visits

There will be a total of 3 follow up visits: 6-8 days, 35 days, and 90 days after ESS. Follow-up visits will consist of appropriate standard of care treatment for subjects. At each follow-up visits a nasal endoscopy will be performed and endoscopic videos will be obtained. Any potentially device related complications will be assessed, concomitant medication will be recorded. During the follow up period, subjects may receive any medication the Investigator deems necessary. Prescription of a new medication will not exclude further participation.

As a standard of care, all patients will fill out the SNOT-22 quality of life questionnaire at their 90 day visit.

8.9 Unscheduled Visits

It is at the discretion of the Investigator to have the subject return to the study site prior to any regular scheduled visit if, for example, the subject experienced an adverse event and/or it is in the best interest of the subject for whatever reason. Evaluation of subjects during an unscheduled visit should include a nasal endoscopy if possible. All other evaluation and testing will be decided by the investigator based on the presenting issue(s) and should be documented.

9 SUBJECT DISCONTINUATION

Subjects may be discontinued from the study for any of the following reasons (but are not limited to):

- Adverse event
- Significant protocol deviation
- Subject noncompliance
- Subject voluntary withdrawal
- Investigator judgment (e.g., inter-current medical problem)
- Lost to Follow-up – for a subject to be considered lost to follow-up 3 documented attempts to contact the subject shall be made by phone and a certified letter shall be sent.

A subject may discontinue voluntarily at any time, for any reason during their participation in the study. If a subject decides to discontinue participation and withdraw from the study, an attempt shall be made to obtain information about any adverse events or reasons for discontinuation. The investigator may withdraw a subject from treatment if, in his/her judgment, it is in the subject's best interest to do so. The investigator shall record the reason for subject discontinuation on the appropriate CRF. Discontinued subjects may be replaced with another enrolled subject.

Intent to treat occurs once all eligibility criteria have been met and informed consent has been signed and an attempt is made to place the device into the treatment space. Any discontinued subject will be followed for as long as possible and any safety and effectiveness results will be included in the final analysis and report.

10 RISK/BENEFIT ASSESSMENT

10.1 Potential Risks

There are two potential sources of risks that can be derived from the use of the Restora spacer: 1) due to the spacer material and shape and 2) due to the drug loaded onto the spacer.

The risks associated with the spacer material itself is considered minimal as the material is biocompatible for its intended use and the material shape (thickness, and area) is similar to that of the standard Silastic Silicone sheet that is used surgically.

The risk associated with the drug is comparable to that with the use of the commercially available Intersect Propel stent, as the amount of drug loaded on Restora™ is equivalent to that loaded onto Propel Stent, 370 μ gm. In addition, the anti-inflammatory steroid, Mometasone Furoate (active ingredient in Nasonex) has been approved for intra-nasal delivery since 1997. The recommended daily dose delivered for treatment of allergies is 2 sprays per nostril per day and for polyposis is 2 sprays per nostril twice a day. Each spray dose is 50 μ g. Therefore, the total maximum recommended dose for the spray user is 400 μ g per day and total of 2,800 μ g over a 7 day period. Compared with this recommended dose, the dose of Mometasone Furoate delivered by Restora is at least 7 fold less than that for the Nasonex.

The potential risks of study participation fall into the following categories:

Frequent: expected to occur in more than 25% of people (more than 25 out of 100 people)

Probable: expected to occur in 10-25% of people (10-25 out of 100 people)

Occasional: expected to occur in 1-10% of people (1-10 out of 100 people)

Remote: expected to occur in less than 1% of people (less than 1 out of 100 people)

Incredible: expected to occur in less than 0.1% of people (less than 1 out of 1000 people).

The risks and possible side effects may include the following:

1. Device Risks

- Premature Displacement of spacer post placement – Remote
- Swallowing of spacer – Incredible
- Adherence of crusting to the implant, resulting in or contributing to sensation of pain/pressure/headache - Occasional
- Foreign body response, including formation of granulation tissue - Remote
- Choking- Incredible

2. Drug Risks

- Nasal irritation and burning - Remote
- Intranasal bleeding - Remote
- Localized infection (bacterial, fungal, or viral) in the nose or pharynx – Occasional
- Nasal Dryness - Incredible
- Glaucoma/elevation of intraocular pressure - Incredible
- Cataracts/change in lens opacities - Incredible

3. General Side Effects with Steroids

- Alteration of the HPA axis including growth suppression (steroid modulation) - Incredible
- Immunosuppression - Incredible
- Headache - Incredible
- Epistaxis - Incredible
- Coughing - Incredible
- Arthralgia - Incredible
- Myalgia – Incredible
- Fatigue - Occasional

4. Nasal Endoscopy is part of routine care associated with rhinosinusitis. These risks may include mild discomfort or light bleeding.

5. The standard risks associated with general anesthesia.

6. An unexpected risk could emerge.

Risks associated with the use of the SinuSys Restora Spacer are anticipated to be similar to those experienced by patients undergoing placement of other non-resorbable spacers and less than that of Propel stent due to its non-resorbable nature. The potential clinical benefits of the Restora Spacer are believed to exceed any residual risks associated with the use of the Restora Spacer.

10.2 Potential Benefits of Study Participation

There may be no direct benefits of study participation. However, subjects will undergo an enhanced level of clinical scrutiny compared to routine clinical care, which may provide some indirect health benefits.

In addition, there could be a benefit of using a drug-eluting spacer post ESS to decrease rate of synechiae formation, and frequency of postoperative interventions, including lyses of adhesions and debridement.

This study is intended to confirm the feasibility of the use of the Restora Nasal Spacer for this purpose.

10.3 Risk/Benefit Conclusions

Based upon the Risk/Benefit analysis performed, the benefits associated with the Restora Nasal Spacer is expected to outweigh the potential risks to the patient.

11 ADVERSE EVENTS / COMPLICATIONS

11.1 Serious Adverse Event (SAE)/Unanticipated Adverse Device Effect (UADE) Definition

Serious Adverse Event (SAE): A SAE is defined as any untoward medical occurrence that:

- Results in death,
- Is life-threatening,
- Requires inpatient hospitalization or prolongation of existing hospitalization
- Results in medical or surgical intervention to prevent life threatening illness
- Results in injury or permanent impairment to a body structure or a body function
- Results in persistent or significant disability/incapacity

Also in the category of SAE is:

- Any other unanticipated serious problem caused by or associated with the device that relates to the rights, safety, or welfare of subjects [21 CFR 812.3(s)]

Important medical events that may not result in death, be life-threatening, or require hospitalization may be considered a SAE when, based upon appropriate medical judgment, they may jeopardize the subject or may require medical or surgical intervention to prevent one of the outcomes listed above. Elective hospital admission will not be considered an SAE for this study.

Unanticipated Adverse Device Effect (UADE) is any serious adverse effect on health or safety, any life-threatening problem or death caused by, or associated with a device, if that effect, problem, or death was not previously identified in nature, severity, or degree of incidence in the application; or any other unanticipated serious problem associated with a device that relates to the rights, safety, or welfare of subjects.

All SAE/UADEs will be collected from first application of the treatment product at the baseline visit until study exit.

11.2 Adverse Event/Adverse Device Effect Relationship to Study Device

The relationship of an event to study device will be documented by the investigator as follows:

Unrelated: The event is clearly related to other factors such as the subject's clinical state, other therapeutic interventions or concomitant drugs administered to the subject. Note, it is not necessary to record in the CRFs these unrelated events.

Possible: The event follows a reasonable temporal sequence from the time of treatment product administration, but could have been produced by other factors such as the subject's clinical state, therapeutic interventions or concomitant drugs.

Probable: The event follows a reasonable temporal sequence from the time of treatment product administration, and follows a known response pattern to the treatment product. The event cannot be reasonably explained by other factors such as the subject's clinical state, therapeutic interventions or concomitant drugs.

Definite: The event follows a reasonable temporal sequence from the time of treatment product/device administration, follows a known response pattern to the treatment product/device, cannot be reasonably explained by other factors such as the subject's condition, concomitant drugs or therapeutic interventions, AND either occurs immediately following treatment product administration, improves on stopping the treatment product, or reappears on re-exposure of the treatment product/device.

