11.3 Procedure for Recording and Reporting Adverse Device Effects

All SAEs and all possibly device related AE/ADEs will be collected from first application of the study treatment products at the baseline visit until study exit.

Beginning with the first study treatment, the investigator will determine whether any SAEs or possibly device related adverse experiences have occurred by evaluating the subject's signs, symptoms, and other test results or assessments.

All SAEs and possibly device related AEs / complications and ADEs (expected or unexpected) which occur during the specified study period, whether observed by the investigator or by the subject, and whether or not thought to be related to treatment product or to study procedures, will be reported in detail on the appropriate CRF and followed until resolution, stabilization, or death, according to Good Clinical Practice (GCP). The record of the SAE/ADE will include a description of the event, start date, stop date, duration, outcome, intensity, if it was serious, relationship to treatment product or study procedure (i.e., causality), change in dosage or discontinuation of treatment product, if treatment was required and if the subject died. The investigator must verify this information.

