11.4 Procedures for Reporting a Serious Adverse Event/Unanticipated Adverse Device Effect

It is the responsibility of the Investigators to inform their IRB about serious adverse events or other events as required by their IRB procedures and in compliance with the applicable regulations.

The investigator should inform SinuSys either by phone or email, within 24 hours of the investigator becoming aware of the event. SAE/UADEs shall be initially reported to:

Name: [name]
Title: Director, Preclinical and Clinical Development
Address: SinuSys Corp, [name]
[contact]
Email: [contact]

A full investigation of any SAE/UADE will be conducted by the Investigator in collaboration with SinuSys Corporation. The Investigator shall report the results of such evaluation to the IRB within 10 working days after notice of the effect. Only Unanticipated possibly device related complications will need to be considered for possible reporting to the FDA. Please consult with regulatory counsel for guidance.

If principal investigator determines that an SAE/UADE presents an unreasonable risk to subjects, the investigation must be terminated as soon as possible, but no later than 5 working days after the investigator makes this determination.

All subjects with an SAE/UADE must be followed up and the outcomes reported. The Investigator should supply SinuSys Corporation and the IRB with any additional requested information (e.g., hospital discharge summary, autopsy report, pathology report, operative report, terminal medical report, etc).

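### Sections 11.2 and 11.3 give conflicting CRF rules for serious adverse events judged unrelated to the device

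*Combined protocol and SAP*

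**What the plan says.** Section 11.1 defines an SAE by outcome. Its main definition opens "A SAE is defined as any untoward medical occurrence that", followed by a list of seriousness criteria, so it does not turn on cause. On collection it says: "All SAE/UADEs will be collected from first application of the treatment product at the baseline visit until study exit".

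Section 11.2 sets out four causality categories. The first reads "Unrelated: The event is clearly related to other factors such as the subject's clinical state, other therapeutic interventions or concomitant drugs administered to the subject", and the note attached to it says that "it is not necessary to record in the CRFs these unrelated events". Seriousness is not mentioned in either sentence.

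Section 11.3 sets the collection scope as "All SAEs and all possibly device related AE/ADEs will be collected from first application of the study treatment products". It then says that these events, "whether or not thought to be related to treatment product or to study procedures, will be reported in detail on the appropriate CRF", with causality as one of the items in the record.

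Section 11.4 adds a route that does not use the CRF: "The investigator should inform SinuSys either by phone or email, within 24 hours of the investigator becoming aware of the event". It also requires a full investigation of any SAE or UADE, and follow-up of the subjects concerned with outcomes reported.

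The safety criterion in section 12.3 has two parts: no UADE while the spacers are in place, and an acceptable overall rate of device related complications.

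**The concern.** An SAE that the investigator judges unrelated falls under two instructions. One waives the CRF entry and the other requires it. An investigator who relies on 11.2 could omit the event, so that a causality opinion decides whether a serious event enters the CRF dataset at all. Causality is normally assessed on events already recorded, so that the opinion can be revisited. An event missing from the dataset cannot be re-adjudicated from that dataset.

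The setting makes this a practical possibility. Every patient has sinus surgery, section 10.1 lists general anaesthesia among the risks, and section 8.7 has all patients on oral antibiotics while the spacers are in place. The unrelated category expressly covers other interventions and concomitant drugs, so another explanation will often be at hand. Each patient also carries both spacers, and section 8.3 keeps the assessing Principal Investigator blind to side, which may make an early causality call harder to get right.

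**Working it through.** No arithmetic applies. The protocol gives no expected SAE rate and no figure that depends on this rule. The check is to take each type of event and read the two recording rules against it.

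| Event type | 11.2 note | 11.3 | Consistent? |
|---|---|---|---|
| Non-serious, judged unrelated | CRF entry not needed | Outside the collection scope | Yes |
| Non-serious, possibly, probably or definitely related | Note does not apply | CRF entry required | Yes |
| Serious, possibly, probably or definitely related | Note does not apply | CRF entry required | Yes |
| Serious, judged unrelated | CRF entry not needed | CRF entry required | No |

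The conflict is confined to the last row. Four further readings fix how much weight it bears.

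1. **Strength of the 11.2 wording.** The note permits omission; it does not forbid recording. An investigator who records the SAE breaches neither section. One who omits it can point to 11.2 but breaches 11.3.

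2. **Section 11.1.** It supports full collection of SAEs but mentions neither the CRF nor relatedness in that sentence. The direct conflict is therefore between 11.2 and 11.3.

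3. **Section 11.4.** The 24-hour notice, the investigation and the follow-up do not depend on CRF entry. They are a second route by which the sponsor learns of the event. Neither 11.4, the analysis sections (12.2 and 12.3) nor section 19 says that these notices are reconciled with the CRFs or used in the analysis. Section 19 provides for an audit trail of changes to the data, but describes no check for events that were never entered.

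4. **Section 12.3.** Both parts of the safety criterion depend on device causality. An SAE correctly judged unrelated counts in neither, recorded or not. The criterion changes only if the judgment was wrong and would have been reversed on review.

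**The case against.** The strongest reply is that this is a drafting slip with a natural consistent reading. Section 11.3 is the section on recording and reporting, and it is explicit and mandatory. Section 11.2 defines causality terms, and its note can be read as restating that non-serious unrelated events lie outside the collection scope, on which both sections agree. On that reading only the word non-serious is missing. The reply adds that 11.4 brings every SAE to the sponsor within 24 hours and has it investigated.

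Much of this stands. The intended rule is probably that of 11.3, and 11.4 is a real safeguard. But the note as written has no such limit, the protocol gives no order of precedence, and it does not connect the 11.4 notices to the CRF data.

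A reader might infer more than the text supports, in three ways:

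- **That no record of the event would remain, or that the omission could never be put right.** Section 11.4 contradicts this. The exposure is to the CRF dataset.
- **That the safety rate in 12.3 is biased downwards.** That rate concerns device related events. Correctly classified unrelated SAEs do not belong in it.
- **That the effect can be sized from the 49 patients, at 1/49 = 2.0 percentage points per missing event.** The division is right, but it describes an all-cause SAE rate, which is neither a listed endpoint nor part of the acceptance criterion. Any number of missing events would also be an assumption.

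**Conclusion.** Wrong as written: an internal contradiction, of low severity. Sections 11.2 and 11.3 cannot both govern the CRF entry of an SAE judged unrelated, and the protocol does not say which does. The consequence is a risk that such events are absent from the CRF safety data and so not open to re-adjudication there; it is not a certain loss. The 12.3 criterion is exposed only through misclassified events, so no numerical magnitude is claimed.

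The conclusion rests on two assumptions: that the safety analysis draws on the CRFs, since no other source is named for it, and that no reconciliation procedure exists beyond what the protocol describes. If the sponsor's procedures already match the 24-hour notices to the CRFs, the practical risk largely disappears, though the text would still need correcting. Leaving non-serious unrelated events unrecorded is applied consistently in both sections and is not challenged here.

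**What to change.** Reconcile 11.2 with 11.3. Limit the 11.2 note to non-serious events, and state there that every SAE is entered on the CRF with its relatedness category, including those judged unrelated. This matches what 11.3 already requires and keeps the causality opinion as a recorded item that can be reviewed later. The cost is one sentence in the protocol and a few more CRF entries. Treatment, visits and endpoints are unaffected.
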